10.5.2 General guidelines for reporting adverse events

- Patients for whom the screening visit of this study is done at the same time as the EOS visit of the previous eliglustat study they were enrolled in, the safety follow-up phone scheduled 30-37 days after the EOS visit of the previous study will not be done. Instead, these patients will be monitored according to the standard safety procedures of this study. The Ethics Committees (and Local Health Authority, if required) at the affected sites will be notified.
- All AEs, regardless of seriousness or relationship to IMP, spanning from the signature of the informed consent form until the end of study visit, or the last IMP administration for patient with early termination, are to be recorded on the corresponding page(s) or screen(s) of the CRF.
- The following categories of medico/surgical events are considered part of the medical/surgical history of the patient and should be entered in the Medical/surgical history CRF:
 - AEs started during the previous study, which are closed at the time of the screening visit and are still considered clinically significant by the investigator at the time of the screening visit.
 - Medical/surgical events started after the follow-up phone call of the previous study and before the ICF signing in the current study, whether ongoing or closed, if they are considered clinically significant by the investigator.
- AEs started during the previous study, which are ongoing at the time of the screening visit should be entered in the AE CRF regardless of whether the patient had a gap in eliglustat

treatment after the end of the previous study, or the end of study visit of the previous study and the screening visit of this study are concomitant.

- Whenever possible, diagnosis or single syndrome should be reported instead of symptoms. The Investigator should specify the date of onset, intensity, action taken with respect to IMP, corrective treatment/therapy given, additional investigations performed, outcome, and his/her opinion as to whether there is a reasonable possibility that the AE was caused by the IMP or by the study procedure(s).

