11 STATISTICAL CONSIDERATIONS

11.1 DETERMINATION OF SAMPLE SIZE

This study will enroll all eligible patients having completed one of the Phase 2 or Phase 3 trials (approximately 32 patients).

This is an extension study. No sample size calculation has been performed. The patients who will be enrolled have already been receiving the IMP for approximately 4 to 8 years prior to the start of the study. The aim of the study is to continue collecting long term data on the efficacy and safety of the IMP.

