### ***Observation period***

The observation period will be divided into 4 periods:

- The **pre-treatment period** is defined as the time from the signed informed consent to first dose of IMP administration in this study.
- The **treatment-emergent period** is defined as the time from the first administration of the IMP to the last administration of the IMP + 5 days. The treatment-emergent period includes the following 2 periods:
  - The **on-treatment period** is defined as the period from the first IMP administration to the last administration of the IMP + 1 day.
  - The **residual treatment period** is defined as the time from the last administration of IMP to the end of the treatment-emergent period.
- The **post-treatment period** is defined as the period from the end of treatment-emergent period.

The treatment-emergent adverse event (TEAE) observation period includes both on-treatment and residual treatment periods.

The on-study observation period is defined as the time from screening until the end of the study (defined as last protocol planned visit or the resolution/stabilization of all serious adverse events [SAEs] and adverse events of special interest [AESIs]).

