### ***2.1.4.1 Adverse events variables***

#### ***Adverse event observation period***

- Pre-treatment adverse events are adverse events that developed or worsened or became serious during the pre-treatment period.
- Treatment-emergent adverse events (TEAEs) are adverse events that developed or worsened or became serious during the treatment-emergent period (treatment-emergent adverse event observation period).
- Post-treatment adverse events are adverse events that developed or worsened or became serious during the post-treatment period.

Continuous monitoring will be performed for (S)AEs and concomitant medications. Results of pregnancy testing for female patients of childbearing potential will be collected. Patients with an SAE or AESI should be followed until event resolution or when follow-up is no longer considered medically necessary, or the patient is lost to follow-up.

All adverse events (including SAEs and AESIs) will be will be coded to a lower-level term (LLT), preferred term (PT), high-level term (HLT), high-level group term (HLGT), and associated primary system organ class (SOC) using the version of Medical Dictionary for Regulatory Activities (MedDRA) currently in effect at Sanofi at the time of database lock.

Adverse events (including serious adverse events and adverse event of special interest) will be recorded from the time of signed informed consent until the end of the study.

Any SAE (including death) brought to the attention of the Investigator at any time after the end of the study for the patient and considered by him/her to be caused by the IMP with a reasonable possibility, should be reported to Global Pharmacovigilance department and will not be recorded in the clinical database.

Serious adverse events and adverse events of special interest (AESI) are defined in the protocol (refer to protocol Section 10.5.1.2 and 10.5.1.3). AESI will be identified and summarized based on CRF information, not standardized or customized MedDRA queries.

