## 2.4 STATISTICAL METHODS

Analysis will be performed on safety and efficacy endpoints at 2 points in this study:

- After the last patient enrolled has completed 2 years of treatment (two-year analysis period)
- At the study completion

Both efficacy and safety results will be calculated both in reference to study entry (study period) and to first eliglustat treatment (eliglustat treatment period). Because patients will enter this study having been treated with eliglustat for various durations, two baselines will be used:

- Study baseline, defined as status at study entry, which is the last non-missing value before the first dose of eliglustat of this study; and
- Eliglustat baseline, defined as status at first dose of eliglustat in the previous Phase 2 or Phase 3 studies. The definition of eliglustat baseline should be the last non-missing value prior to first dose of eliglustat in prior studies.

The eliglustat baseline can only be obtained if the assessments in EFC13781 study and the previous studies are comparable. Assessment method, location, parameters, result evaluation, etc should be considered for comparability check if applicable. In addition, eliglustat baseline definition of hemoglobin and platelet for Phase 2 and ENCORE study were defined separately in [Section 2.5.2](#).

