#### ***Analysis of all treatment-emergent adverse event(s) leading to permanent treatment discontinuation***

- All treatment-emergent adverse events leading to permanent treatment discontinuation, by primary SOC, HLGT, HLT, and PT, showing the number (%) of patients sorted by the internationally agreed SOC order. The other levels (HLGT, HLT, PT) will be presented in alphabetical order
- By-patient listing of all treatment-emergent adverse events leading to permanent treatment discontinuation

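### Unchanged adverse events carried over from the feeder study reach no SAP adverse event table or listing, and the feeder safety call is cancelled even for patients who are then not dosed

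*Protocol*

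**What the plan says.** Every patient comes from an earlier Phase 2 or Phase 3 eliglustat study, called the feeder study here.

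- **Recording.** Protocol 10.2.1.1 and 10.5.2 state that "AEs started during the previous study, which are ongoing at the time of the screening visit should be entered in the AE CRF", with or without a gap in treatment between the studies. Feeder AEs go to medical history only if they are closed and still considered clinically significant.
- **Classification.** Under SAP 2.1.4 the pre-treatment period "is defined as the time from the signed informed consent to first dose of IMP administration in this study". SAP 2.1.4.1 then sets the classes: "Pre-treatment adverse events are adverse events that developed or worsened or became serious during the pre-treatment period"; treatment-emergent AEs (TEAEs) "are adverse events that developed or worsened or became serious during the treatment-emergent period"; post-treatment AEs follow the same pattern for the period after that.
- **Reporting.** The overviews, tables and listings in SAP 2.4.5.1 are built class by class. The analysis of AEs that end treatment covers "all treatment-emergent adverse event(s) leading to permanent treatment discontinuation". Only the first death table, in SAP 2.4.5.2, is free of any class. Protocol 11.4.3 commits to summarising every AE. SAP 1.5 records no modification of the protocol's statistical section, and SAP 1.6 mentions only a clarified treatment-emergent period.
- **Follow-up call.** If screening takes place at the feeder end-of-study visit, Protocol 10.5.2 says that "the safety follow-up phone scheduled 30-37 days after the EOS visit of the previous study will not be done". The reason given is that this study's safety procedures take over. Those procedures include a contact about every 4 weeks (Protocol 1.2, footnote g). Screening may last up to 45 days (Protocol 10.2.1).

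**The concern.** The recording rule and the analysis rule do not meet. The protocol sends ongoing feeder AEs to the AE form and away from medical history. The SAP then analyses that form by classes which all start at this study's consent. Long-lasting, stable AEs that began on eliglustat are of direct interest in an extension whose patients have had about 4 to 8 years of treatment, and safety is a stated secondary objective. As written, these events would be collected and then left out of every AE display.

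The cancelled call has a similar fault. It is withdrawn because another form of monitoring replaces it, but the rule is not limited to patients who go on to receive that monitoring.

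**Working it through.** No sample size or power figure bears on this point. The check compares rules, with two small pieces of arithmetic.

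**Step 1. Run a carried-over AE through the SAP classes.**

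| Carried-over AE on the AE form | Class | Where it appears |
|---|---|---|
| Worsens or turns serious between consent and first dose | Pre-treatment | Pre-treatment overview and listing |
| Worsens or turns serious between first dose and last dose + 5 days | TEAE | TEAE tables and listings |
| Worsens or turns serious later | Post-treatment | Post-treatment overview and listing |
| Onset missing, or incomplete without pointing to a start before treatment | TEAE by default (SAP 2.5.3) | TEAE tables and listings |
| Known onset before consent, unchanged | None | No AE table or listing, unless fatal (SAP 2.4.5.2) |

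The gap is the last row only. Medical history does not catch these events, because the protocol sends only closed feeder AEs there.

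**Step 2. Follow such an AE to a treatment stop.** SAP 2.2 counts permanent discontinuations by main reason and lists the reasons by patient, whatever the AE class. The AE discontinuation table, its listing and the matching overview row count TEAEs only. The patient is therefore in the first display and absent from the second.

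Illustration for the AE table alone, assuming one such patient among the approximately 32 planned: 1/32 = 0.031, so the table shows 0% where 3.1% stopped for an AE. The documents do not say whether any such patient exists.

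**Step 3. Timing of contacts.** Take the combined feeder end-of-study and screening visit as day 0, and assume that the 4-weekly contacts are counted from it.

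- Feeder call, if kept: days 30 to 37.
- First contact in this study: 4 × 7 = day 28. Second: 8 × 7 = day 56.
- Latest end of screening: day 45.

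A patient who fails screening before about day 28 has no scheduled contact in this study and no feeder call. One who fails between about day 28 and day 45 has had at most one contact, since day 56 lies beyond the window. If the 4-weekly contacts start only at Day 1 of this study, no screen failure has any.

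**Step 4. What else covers an undosed patient.** AE recording in Protocol 10.5.2 runs to the end-of-study visit or the last dose, and a screen failure has neither here. The remaining provisions are:

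- pregnancy follow-up (Protocol 10.5.1.3);
- follow-up of AEs already recorded (10.5.2);
- drug-related SAEs that come to the investigator's notice later (10.5.3);
- listing of safety data from patients outside the safety population (SAP 2.4.5).

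None of these schedules a contact to find a new event. Clinically significant laboratory abnormalities at Visits 1 and 2 go to medical history (10.2.1.1), and 10.5.2 treats laboratory findings as AEs only after Day 1. A failure on the liver tests in E04 may therefore leave no AE to follow.

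**The case against.** The strongest reply is that little goes missing. The events are on this study's AE form and were already AEs of the feeder study. Keeping an unchanged old event out of a TEAE table is correct practice. Protocol 10.6 and 10.7 commit the report to all safety observations and events. The study is descriptive, and the remaining gap is narrow. Most of this stands, and it limits the point to omission from the planned displays. It does not supply a display: no SAP table or listing carries out the protocol's commitment for these events.

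A reader might infer several stronger things that the documents do not support.

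- **That safety data are lost.** They are recorded. They are not reported by the SAP's AE displays.
- **That the study report under-counts AE-related stopping.** Disposition by main reason and the by-patient listing of reasons still show the stop, and Protocol 7.3 promises a summary of all discontinuations. Only the TEAE-based displays leave it out.
- **That SAP 2.4 makes these events treatment-emergent, because it refers safety results to first eliglustat treatment.** That text introduces two baselines for values and changes. AE periods are defined separately, from this study's consent and first dose.
- **That a screen failure on a positive pregnancy test goes unfollowed.** Protocol 10.5.1.3 makes pregnancy follow-up mandatory after consent.
- **That every rollover screen failure goes without contact in either study.** A patient who fails after about day 28 may already have been contacted. The feeder protocols are not available, so a fallback there cannot be ruled out, although the cancellation itself carries no condition.

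**Conclusion.** Both gaps hold in limited form.

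First, a feeder AE with a known onset before consent that is ongoing at screening and neither worsens nor turns serious enters the AE form but meets no SAP class. It appears in no SAP AE table or listing unless fatal. That conflicts with Protocol 11.4.3, and SAP 1.5 does not declare it. Where such an AE ends treatment, disposition and the AE discontinuation table can disagree by 3.1 points per patient, taking 32 patients.

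Second, the cancellation of the feeder call reaches patients to whom its stated reason does not apply. Those who fail screening before about day 28 have no scheduled contact here for new events. This is an omission in the text and not a stated rule against follow-up. It rests on counting the 4-weekly contacts from the screening visit and on there being no fallback in the feeder protocols.

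How many events or patients are affected cannot be derived from the documents. The changes are worth making because they are cheap and safety is a stated objective.

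**What to change.** 1. In SAP 2.1.4.1 add a category for AEs ongoing from the feeder study, meaning AE form entries with onset before consent to this study. Give it a count by SOC and PT and a by-patient listing. The TEAE definition stays as it is.
2. In SAP 2.4.5.1 base the table of AEs leading to permanent discontinuation on all AE form entries with that action taken, and show TEAEs as a sub-row. It can then be reconciled with disposition.
3. In Protocol 10.5.2 reconcile the cancellation with its reason by limiting it to patients who are dosed and so enter this study's safety monitoring. The call that the feeder study had already planned then stands for the others.

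Cost: SAP wording, one table and one listing from data already collected, a protocol clarification, and one already planned call for each rollover patient who is not dosed.

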10.5.3 Instructions for reporting serious adverse events

In the case of occurrence of an SAE, the Investigator must immediately:

- ENTER (within 24 hours) the information related to the SAE in the appropriate screens of the e-CRF; the system will automatically send a notification to the monitoring team after approval of the Investigator within the e-CRF or after a standard delay.
- SEND (preferably by fax or e-mail) a photocopy of all examinations carried out and the dates on which these examinations were performed, to the representative of the monitoring team whose name, fax number, and email address appear on the clinical trial protocol. Care should be taken to ensure that the patient's identity is protected and the patient's identifiers in the clinical trial are properly mentioned on any copy of a source document provided to Genzyme. For laboratory results, include the laboratory normal ranges.
- All further data updates should be recorded in the e-CRF as appropriate, and further documentation as well as additional information (for laboratory data, concomitant

medications, patient status, etc.) should be sent (by fax or e-mail) to the monitoring team within 24 hours of knowledge of the SAE. In addition, every effort should be made to further document any SAE that is fatal or life threatening within a week (7 days) of the initial notification.

- A back-up plan (using a paper CRF process) is available and should be used when the e-CRF system does not work.

Any SAE brought to the attention of the Investigator at any time after the end of the study for the patient and considered by him/her to be caused by the IMP with a reasonable possibility, should be reported to GPE.

10.5.4 Guidelines for reporting adverse events of special interest

For AESIs, Genzyme must be informed immediately (ie, within 24 hours), as per SAE notification guidelines described in [Section 10.5.3](#), even if not fulfilling a seriousness criterion, using the corresponding pages of the CRF (to be sent) or screens in the e-CRF. Instructions for AE reporting are summarized in [Table 2](#).

Table 2 - Summary of adverse event reporting instructions

Event category	Reporting timeframe	Specific events in this category	Case Report Form completion		
			AE form	Safety Complementary Form	Other specific forms
Adverse Event (non-SAE, non-AESI)	Routine	Any AE that is not SAE or AESI	Yes	No	No
Serious Adverse Event (non-AESI or AESI)	Expedited (within 24 hours)	Any AE meeting seriousness criterion per Section 10.5.1.2	Yes	Yes	No
Adverse Event of Special Interest	Expedited (within 24 hours)	Pregnancy and any AE listed in Section 10.5.1.3	Yes	Yes	Yes

10.6 OBLIGATIONS OF THE SPONSOR

During the course of the study, Genzyme will report in an expedited manner:

- All SAEs that are both unexpected and at least reasonably related to the IMP (SUSAR), to the regulatory authorities, IECs/IRBs as appropriate and to the Investigators.
- All SAEs that are expected and at least reasonably related to the IMPs to the regulatory authorities, according to local regulations.

Any other AE not listed as an expected event in the Investigator's Brochure will be considered unexpected.

Genzyme will report all safety observations made during the conduct of the trial in the clinical study report.

10.7 ADVERSE EVENTS MONITORING

All events will be managed and reported in compliance with all applicable regulations, and included in the final clinical study report.

11 STATISTICAL CONSIDERATIONS

11.1 DETERMINATION OF SAMPLE SIZE

This study will enroll all eligible patients having completed one of the Phase 2 or Phase 3 trials (approximately 32 patients).

This is an extension study. No sample size calculation has been performed. The patients who will be enrolled have already been receiving the IMP for approximately 4 to 8 years prior to the start of the study. The aim of the study is to continue collecting long term data on the efficacy and safety of the IMP.

11.2 DISPOSITION OF PATIENTS

Screened patients are defined as any patient who met the study criteria and signed the informed consent.

11.3 ANALYSIS POPULATIONS

11.3.1 Efficacy populations

Primary and secondary efficacy will be evaluated in the Full Analysis Set population (FAS) defined as all patients enrolled who receive at least 1 dose of eliglustat treatment in this study.

11.3.2 Safety population

Safety analyses will be performed on the Safety Set, which is equivalent to the FAS for this study.

11.3.3 Pharmacokinetic population

Pharmacokinetic (PK) population: a subset of safety population containing patients who have at least one PK sample taken. Patients will be analyzed in the treatment group corresponding to those defined in the safety population.

11.4 STATISTICAL METHODS

All endpoints will be summarized descriptively; no hypothesis testing will be performed. Descriptive statistics include those for continuous (n, mean, median, minimum, maximum), categorical (n, percent), cumulative incidence (n, percent) or incidence rate (n/year) outcomes, as appropriate. Calculations and summaries will include all non-missing data at a given time point, imputation will not be performed.

Analysis will be performed on safety and efficacy endpoints at 2 points in this study:

- After the last patient enrolled has completed 2 years of treatment (two-year analysis period)
- When the study is complete

For the PAP, response will be calculated both in reference to study entry (study period) and to first eliglustat treatment (eliglustat treatment period). Because patients will enter this study having been treated with eliglustat for various durations, two baselines will be used:

- Study baseline, defined as status at study entry; and
- Eliglustat baseline, defined as status at first dose of eliglustat in the previous Phase 2 or Phase 3 study.

In reference to the study period, skeletal response will be evaluated for all patients at the 2 year point by measured values (eg, category of bone pain, or bone density value in g/cm²) and changes from baseline (eg, shift in category of bone pain or absolute and percent change from baseline in BMD g/cm² or incidence over 2 years, as appropriate).

In reference to the period of eliglustat treatment, skeletal response will be evaluated 2 years after study entry, but results will be grouped by duration of eliglustat treatment at the time of analysis. The actual groupings will depend on the distribution of treatment duration at the time of analysis, eg, 6 yr., 7 yr., 8 yr. or 6-8 yr., 8-10 yr.

When the study has completed, summaries will be performed for both the total on-study period, and the eliglustat treatment period, as described above.

11.4.1 Extent of study treatment exposure and compliance

The extent of study treatment exposure and compliance will be assessed and summarized by actual treatment received within the safety population.

Duration of IMP exposure is defined as: last dose date – first dose date + 1 day, regardless of unplanned intermittent discontinuations.

A given period of administration will be considered noncompliant if the patient takes less than 90% or more than 105% of the planned dose of treatment as required by the protocol. No imputation will be made for patients with missing or incomplete data. Treatment compliance, above-planned and under-planned dosing percentages will be summarized descriptively (N, Mean, SD, Median, Min, and Max). The percentage of patients with compliance categorized as <80%, 80%-90%, 90%-105%, >105% will be summarized.

